4.4 Potential risks and benefits

The healthy volunteers will not derive any therapeutic benefit from participating in the study. However, every effort will be made to minimize potential risk(s) to subjects participating. Emapalumab is approved by FDA since November 2018, for the treatment of patients with primary HLH who have refractory, recurrent or progressive disease or intolerance with conventional HLH therapy.

Since the start of the clinical development program for emapalumab, more than 100 patients have received emapalumab in clinical trials and through compassionate use. Furthermore, more than 70 patients have been treated to date in the US following FDA approval, and post-marketing surveillance has not revealed any additional safety concerns with the use of emapalumab. Based on the analyses conducted to date, no sign of any off-target effect of emapalumab has been detected.

Subjects in the proposed phase I study will receive a single dose of 1 mg/kg, as compared with dose up to 10mg/kg used in other studies with no safety concerns.

Potential risks based on emapalumab's mechanism of action are presented below.

- Infusion related reactions and hypersensitivity
Up to the 24-Aug-2019, cumulatively, a total of 1290 emapalumab infusion have been administered in clinical trials and 13 of the 62 study subjects (21.0 %) treated had experienced at least 1 IRR. No serious hypersensitivity reactions such as anaphylactic or anaphylactoid reactions have been reported. Patients should, however, not be re-exposed to the investigational treatment in case of hypersensitivity to emapalumab or any of the excipients.
The most frequently reported IRRs were cutaneous reactions coded drug eruption, rash or erythema or erythematous rash, hyperhidrosis or pyrexia.
- Majority of IRRs were of mild or moderate intensity. IRRs did not prevent administration of the full dose of emapalumab. All IRRs resolved. No specific premedication is required prior to emapalumab administration.
- Infections

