### 8.4.3 Visit Windows

The visit windows for PK and PD assessments are displayed in Table 1, for Vital signs in Table 2 and for other assessments in Table 3. The analysis time points, based on the visit windows, will be used for analysis. In addition, let the IMP administration date be Day 1.

For descriptive statistics, in the case a parameter is not available on the specified analysis timepoint, the visit window is to be applied. Priority will be given to scheduled visits; unscheduled visits will be used if no scheduled visits occurred within the analysis visit window.

If there is more than one observation during the visit window, a value will be selected as follows: the value closest to the actual analysis timepoint in question (eCRF) will be chosen first. In the case that there are 2 values equidistant to the analysis timepoint of interest, the observation that is before the analysis timepoint in question (eCRF) will be selected. In the case of 2 or more measurements on the same date, the earliest measurement will be selected.

**Table 1** Visit Window of pharmacokinetic and pharmacodynamic assessment

Analysis time point		Visit Window	Pharmacokinetics	Pharmacodynamics
Day 1	Preinfusion	Before IMP administration	X	X
	1 hr	55 min to < 65 min	X a)	X
	2 hr	1 hr 55 min to < 2 hrs 5 min	X	X
	4 hr	3.75 hr to <4.25 hr	X	X
	8 hr	7.5 hr to <8.5 hr	X	X
	10 hr	9.5 hr to <10.5 hr	X	X
Day 2		Day 2	X	X
Day 3		Within Day 3	X	X
Day 5		Within Day 5	X	X
Day 8		Within Day 8	X	X
Follow-up Week 2		Day 12 to Day 16	X	X
Follow-up Week 4		Day 26 to Day 30	X	X
Follow-up Week 6		Day 40 to Day 44	X	X
Follow-up Week 8		Day 54 to Day 58	X	
Follow-up Week 10		Day 68 to Day 72	X	
Follow-up Week 12		Day 82 to Day 86	X	
Study Completion Visit (Week 14)		Day 96 to Day 100	X	X
Withdrawal (WD)		When the subject is withdrawn	X	X

a) At end of infusion.

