**Table 4 List of pharmacokinetic parameters**

Parameter	Description	Unit	Display Digits
$C_{\max}$	Maximum observed serum concentration	ug/L	3 significant figures
$t_{\max}$	Time to $C_{\max}$	h	2 decimal places
CEOI	Observed concentration at end of infusion	ug/L	3 significant figures
$AUC_{\text{last}}$	Area under the serum concentration-time curve from time 0 to the time corresponding to the last quantifiable serum concentration $AUC = \int_0^t C$	ug*h/L	3 significant figures
$AUC_{\text{inf\_calc}}$	Area under the serum concentration-time curve extrapolated to infinity, calculated using the formula: $AUC_{\text{inf\_calc}} = AUC_{\text{last}} + Ct/\lambda z$ , where Ct is the predicted concentration at tlast and $\lambda z$ is the apparent terminal phase rate constant. Values of $AUC_{\text{inf\_calc}}$ will only be deemed reliable if $\lambda z$ is reliably estimated and if % AUCextr is less than 20%.	ug*h/L	3 significant figures
%AUCextr	Percentage of extrapolated AUC from T last to infinity time $= \frac{AUC_{\text{INF\_calc}} - AUC_{\text{last}}}{AUC_{\text{INF\_calc}}} \times 100$	%	1 decimal place
$AUMC_{\text{last}}$	Area under the first moment curve from the time of dosing to the last measurable concentration. $AUMC_{\text{last}} = \sum_{i=1}^{\text{last}} (t_{(i+1)} - t_i) \cdot \frac{t_i \cdot C_i + t_{(i+1)} \cdot C_{(i+1)}}{2}$ i=timepoint(1,2,⋯, last)	ug*h*h/L	3 significant figures
$AUMC_{\text{inf\_calc}}$	Area under the first moment curve (AUMC) extrapolated to infinity, based in the last predicted concentration. $= AUMC_{\text{last}} + \frac{t_{\text{last}} - Clast_{\text{pred}}}{\lambda z} + \frac{Clast_{\text{pred}}}{\lambda z^2}$	ug*h*h /L	3 significant figures
$\lambda z$	Terminal rate constant The first-order rate constant for the terminal phase (log-linear) part of the curve. Estimated by linear regression of time-logarithmic concentration. If the number of measurement results with a value greater than 0 and less than 3 points measured after $C_{\max}$ is not calculated by WinNonlin. The associated $R^2$ of the estimate is required to be $>0.8$ in order to be reliably estimated.	1/h	2 decimal places
$t_{1/2}$	Terminal half-life, where $t_{1/2} = \ln(2)/\lambda z$	h	3 significant figures
CL	Total systemic clearance $= \frac{\text{Dose}}{AUC_{\text{INF\_calc}}}$	L/h	3 significant figures

	CL is calculated using dose level (mg/kg) and actual dose (mg).		

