V ss	
Steady state volume of distribution
 
Calculate from the following formula in subjects whose <math>\lambda_z</math> can be calculated.
 $V_{ss} = CL \times MRT_{inf}$ 
Vss is calculated using dose level (mg/kg) and actual dose (mg).
	L	3 significant figures
MRT last	
Average residence time from the start of infusion to the final blood collection time
 $= \frac{AUMC_{last}}{AUC_{last}} - \frac{TI}{2}$ 
TI :Duration of infusion
	h	3 significant figures
MRT inf	
Average residence time from start of infusion to infinite time
 $= \frac{AUMC_{inf\_calc}}{AUC_{INF\_calc}} - \frac{TI}{2}$ 
TI :Duration of infusion
	h	3 significant figures

Subjects will be excluded from the PK analysis if their data do not allow for accurate assessment of the PK (e.g. incomplete administration of the study drug; subject vomited after receiving study drug; missing information of dosing and sampling times; concentration data not sufficient for PK parameter calculation).Following rules will be applied for descriptive statistics.

- Lower Limit of Quantification (LLOQ) will be substituted with 0.
- The number of subject displayed as "N" on summary tables will be the number of subject whose serum concentrations are measured (include LLOQ) or PK parameters are calculated.
- When the time of blood collection is outside the time windows, the relevant serum concentration will be listed but excluded from the calculation of summary statistics.

**Table 5** List of compound and lower limit of quantification

Compound	Unit	Lower Limit of Quantification	Rounding Digit
Emapalumab	ug/L	62.5 ug/L	0.01

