#### 14.1.1 IMP Concentration

Population: PK/PD population

Group: Emapalumab

Contents: 

- Calculate the descriptive statistics of IMP Concentration at each analysis time point (defined in Table 1 in Section 8.4.3 Visit Windows) by groups.

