### 14.2.1 Pharmacodynamic Biomarkers Concentration

Population: PK/PD population

Group: Emapalumab

Contents: • Calculate the descriptive statistics of pharmacodynamic biomarkers concentration in those parameters described in Table 6 in Section 14.2 Pharmacodynamic biomarkers at each analysis time point (defined in Table 1 in Section 8.4.3 Visit Windows) by groups.

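### The PK exclusion examples in SAP 14.1 and the fixed end-of-infusion window in SAP Table 1 do not fit an i.v. infusion that may be slowed or stopped

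*SAP*

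**What the plan says.** **Exclusion rule.** The text after Table 4 in SAP 14.1 removes a subject from PK on one condition, namely data that "do not allow for accurate assessment of the PK (e.g. incomplete administration of the study drug; subject vomited after receiving study drug". Two further examples complete the list: unknown dosing or sampling times, and too few concentrations. The same section, and Protocol 6.7.5.2, base PK parameters on actual dose and actual times.

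**Dosing.** Protocol 6.6.4 gives the product by i.v. infusion over 1 hour, extendable to 2 hours, and records start and end times and the volume infused. Protocol 6.3.1 lets the infusion be slowed, within two hours. Protocol 6.3.1 and 6.5.3.1 foresee stopped infusions and keep those subjects in the study. Protocol 6.6.3 states that PK in healthy adults is linear.

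**Population.** SAP 7.2 admits to the PK/PD population subjects infused with emapalumab who have no deviation affecting PK/PD evaluation. Protocol 9.4 names an incorrect dose among the deviations to be notified.

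**Windows.** SAP Table 1 gives the 1 hr sample a window of 55 to <65 min and marks the PK sample as taken at end of infusion. The 2 hr window is 115 to <125 min. SAP 8.4.3 says that "in the case a parameter is not available on the specified analysis timepoint, the visit window is to be applied". SAP 14.1 says that for a sample outside its window "the relevant serum concentration will be listed but excluded from the calculation of summary statistics".

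**The concern.** Vomiting bears on an oral dose and has no bearing on an infused one. Incomplete administration is listed as an example of data that cannot support PK, yet everything needed to use such data is recorded and the calculation already runs on the dose received. No rule says when a partial infusion is still assessable, so the decision would be made case by case. Only six subjects receive emapalumab and PK is a primary endpoint. Each subject left out is one sixth (16.7%) of the set.

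SAP 14.1 also speaks only of the PK analysis. SAP 14.2.1 then says "Calculate the descriptive statistics of pharmacodynamic biomarkers concentration" without saying how a partly dosed subject is treated, unless SAP 7.2 has already removed that subject.

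The window is a second mismatch. A sample defined by an event, the end of infusion, is placed by the clock. If the infusion is slowed or stopped, a correctly timed sample can miss its window. SAP 8.4.3 and SAP 14.1 can then give different answers on whether it enters the table, so two programmers could produce different summaries from the same data.

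**Working it through.** The plan states no figure of its own to reproduce here.

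**1. Which parameters survive a partial dose.** Under linear PK, giving a fraction f of dose D multiplies every concentration by about f.
- CL = fD / (f × AUCinf) = D / AUCinf: unchanged.
- λz is the slope of log concentration: unchanged, and so is t1/2 = ln 2 / λz.
- MRT = AUMC / AUC − TI/2 and %AUCextr are ratios: unchanged. So is Vss = CL × MRTinf.
- Cmax, CEOI, AUC and AUMC scale with f, and tmax moves with the end of infusion.

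Numerical check. Inputs from Protocol 4.1.2.3: CL 0.007 L/h, central volume 3.02 L, half-lives 1.55 and 25.4 days. These imply a peripheral volume of 2.75 L against 2.83 L stated. Body weight of 60 kg is assumed. NCA uses the linear trapezoidal rule at the Table 1 times, with the last five points for λz.

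| | 60 mg over 1 h | 30 mg over 0.5 h, actual dose |
|---|---|---|
| CL (L/h) | 0.0069 | 0.0069 |
| Vss (L) | 5.59 | 5.59 |
| t1/2 (days) | 25.4 | 25.4 |
| MRTinf (days) | 33.7 | 33.7 |
| %AUCextr | 6.4 | 6.4 |
| CEOI (µg/L) | 19,763 | 9,907 |

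With 70 kg and the stated peripheral volume, full, 75% and 50% doses all give CL 0.00692 L/h, t1/2 25.8 days and Vss 5.67 L.

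**2. Where this stops holding.** The LLOQ is 62.5 µg/L (SAP Table 5). In the 60 kg model:
- At 10% of the dose, Week 14 is only just quantifiable (62.7 µg/L).
- At 5%, the last quantifiable sample is Week 10. CL and t1/2 hold, but %AUCextr is 13.6% and MRTlast is 22.2 days against 26.8.
- At 2%, the last quantifiable sample is Week 4. t1/2 falls to 17.6 days, CL rises by about 18% (0.00819 / 0.00691), and %AUCextr is 33%, which fails the 20% limit in SAP Table 4.

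An assessability condition is therefore needed.

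**3. What losing one of six would cost.** The 95% CI of a geometric mean is GM ×/÷ exp(t × σ / √n), with σ = √ln(1 + CV²). t is 2.571 for n = 6 and 2.776 for n = 5.

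| Assumed CV | n = 6 | n = 5 |
|---|---|---|
| 30% (σ = 0.294) | 1.36 | 1.44 |
| 20% (σ = 0.198) | 1.23 | 1.28 |
| 15% (σ = 0.149) | 1.17 | 1.20 |

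The documents give a CV (within 30%) for parameters such as Cmax and AUC. They give none for CL, Vss, t1/2 or MRT, so the table is an assumption for the parameters that could be kept. For Cmax and AUC, n would be 5 either way.

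**4. The window.** For infusions ending between 60 and 120 min:
- [60, 65) fits the end-of-infusion window: 5 min.
- [65, 115) fits no window: 50 min.
- [115, 120] falls in the 2 hr window: 5 min.

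An infusion stopped before 55 min also fits none. In the 60 kg model a full 60 mg dose gives end-of-infusion values of 19,763 (1 h), 19,711 (1.5 h, −0.3%) and 19,659 µg/L (2 h, −0.5%). Keeping a slowed full-dose sample under end of infusion would hardly move the mean.

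**The case against.** **The rule is conditional and its items are examples.** Subjects leave only if their data cannot support accurate PK, and actual dose and time are already required. This stands. A reader might infer that any incomplete infusion costs a subject, and the text does not say that. But naming incomplete administration as an example points towards exclusion, and nothing sets a limit.

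**SAP 7.2 may already settle it.** If a partial infusion counts as an incorrect dose under Protocol 9.4, the subject is outside the PK/PD population for PK and PD alike. If a stop that the protocol foresees is not a deviation, the subject is inside. The documents do not say which, so SAP 14.1 cannot be amended alone.

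**The dose basis.** SAP Table 4 says that "CL is calculated using dose level (mg/kg) and actual dose (mg" in mg. A reader might infer that a partly dosed subject's CL and Vss would be computed on the nominal 1 mg/kg and inflated. SAP 14.1 and Protocol 6.7.5.2 require actual dose, so that error is not a consequence of the plan.

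**The window hardly matters.** The Table 1 footnote ties the PK sample to end of infusion, SAP 8.4.3 can be read as applying windows only when the scheduled value is missing, and keeping a 90-min value out of a mean labelled 1 hr is defensible. This stands as to size. A reader might infer that CEOI or other NCA parameters are distorted. They are not, because they use actual times. What remains is the conflict between the two rules.

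**It is unlikely to arise.** Protocol 4.4 reports that "IRRs did not prevent administration of the full dose of emapalumab", and Protocol 6.6.3 describes the infusions in the earlier healthy-volunteer study as uneventful. This stands, and it keeps the point minor.

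**Conclusion.** The point holds and is minor. The vomiting example cannot apply to an infused drug. Incomplete administration is too broad an example: when dose and times are known and concentrations stay quantifiable long enough, CL, Vss, λz, t1/2, %AUCextr and MRT remain usable, while the exposure parameters and concentrations are not comparable with a full dose. This rests on the linearity stated in the protocol and on the actual-dose calculation. Loss of a subject is possible, not automatic. If it happened, the CI factor would go from 1.36 to 1.44 at a CV of 30%, or from 1.17 to 1.20 at 15%, both assumed for these parameters.

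The fixed end-of-infusion window can drop or relabel a correctly timed sample. The effect is confined to the by-time-point concentration table and the mean curve. Individual values are listed in any case, and there is no hypothesis test.

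**What to change.** 1. **SAP 14.1, vomiting.** Delete the example.

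2. **SAP 14.1, incomplete administration.** Keep the condition on accurate assessment and replace the example with a rule to this effect:

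   > When administration is incomplete but the dose given and the start and end times are known, CL, Vss, λz, t1/2, %AUCextr and MRT are summarised using the dose received and the actual infusion duration, provided the Table 4 reliability criteria for λz and %AUCextr are met and concentrations are quantifiable long enough to define the terminal phase. That subject's Cmax, tmax, CEOI, AUC, AUMC, concentrations and PD values are listed and left out of summaries and mean plots.

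3. **SAP 7.2.** State that an incomplete infusion with known dose and times does not by itself remove a subject from the PK/PD population, and reconcile this with the deviation wording there and in Protocol 9.4.

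4. **SAP Table 1 and 8.4.3.** Define the end-of-infusion PK window as actual end of infusion ±5 min and summarise the sample under end of infusion. If the infusion ends within the 2 hr window, let the same sample also serve the 2 hr time point. State that for PK concentrations the out-of-window rule of SAP 14.1 governs over 8.4.3.

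This concerns analysis rules only and takes no view on infusion duration or on when an infusion should stop.

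**Cost.** SAP wording, best settled before unblinding. After one incomplete infusion N would differ between parameters (6 for CL and t1/2, 5 for Cmax, AUC and concentrations), so footnotes are needed. SAP 14.1 says that N "will be the number of subject whose serum concentrations are measured (include LLOQ) or PK parameters are calculated"; this must become the number of subjects contributing to each summary.

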#### 14.1.1 IMP Concentration

Population: PK/PD population

Group: Emapalumab

Contents: 

- Calculate the descriptive statistics of IMP Concentration at each analysis time point (defined in Table 1 in Section 8.4.3 Visit Windows) by groups.

#### **14.1.2      Figure of Mean $\pm$ SD of IMP Concentration Versus Time Curves**

Population: PK/PD population

Group: Emapalumab

Contents:

- Create XY plots of Mean  $\pm$  SD of IMP Concentration from before IMP administration and at each analysis time point (defined in Table 1 in 8.4.3 Visit Windows) by groups.
- X axis: Analysis visits defined in Table 1 in Section 8.4.3 Visit Windows
- Y axis: IMP Concentration [ug/L]
- Create the same XY plots with Y axis of log-transformed IMP Concentration.
- When Y axis is log-transformed, its scale will be log base 10 of  $10^{-1}, 10^0, 10^1, 10^2, 10^3, 10^4$ .
- When the Y axis is log-transformed, eliminate LLOQ from the plot.

#### **14.1.3      Figure of IMP Concentration Versus Time Curves of Individual Subjects**

Population: PK/PD population

Group: Emapalumab

Contents:

- Create XY plots of IMP Concentration at actual time points by individual subjects.
- X axis: Actual time points observed
- Y axis: IMP Concentration [ug/L]
- Create the same XY plots with Y axis of log-transformed IMP Concentration.
- When Y axis is log-transformed, its scale will be log base 10 of  $10^{-1}, 10^0, 10^1, 10^2, 10^3, 10^4$ .
- When the Y axis is log-transformed, eliminate LLOQ from the plot.
- For individual concentration-time profiles, concentrations used for the determination of the terminal half-life will be presented.

#### **14.1.4      Pharmacokinetic Parameters**

Population: PK/PD population

Group: Emapalumab

Contents: • Calculate the descriptive statistics of pharmacokinetic parameters defined in Table 4 in Section 14.1 Pharmacokinetic assessment by groups.

## 14.2 Pharmacodynamic Biomarkers

The list of pharmacodynamic biomarkers evaluated in this study are presented in Table 6.

**Table 6 List of pharmacodynamic biomarkers**

Biomarkers	Unit	Lower Limit of Quantification	Rounding Digit
Pre-dose circulating IFN $\gamma$ concentration	pg/mL	50.00 pg/mL	0.01
Total IFN $\gamma$ concentrations	pg/mL	50.00 pg/mL	0.01
CXCL9 concentration	pg/mL	80.00 pg/mL	0.01
sIL2R concentration	pg/mL	50.00 pg/mL	0.01

Following rule will be applied for descriptive statistics.

- Lower Limit of Quantification (LLOQ) will be substituted with 0.

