4.1.2.3 Clinical Data

Since the start of the clinical development program for emapalumab, more than 100 patients have received emapalumab in clinical trials and through compassionate use. Furthermore, more than 70 patients have been treated to date in the US following FDA approval, and post-marketing surveillance has not revealed any additional safety concerns with the use of emapalumab.

Emapalumab has been granted Orphan Drug Designation in the United States (US) on 26 March 2010 and in Europe (EU) on 09 June 2010. Emapalumab has obtained Breakthrough designation in US on 11 March 2016 and PRIME designation in EU on 26 May 2016.

On 20 November 2018 the FDA approved emapalumab for the treatment of adult and pediatric (newborn and older) patients with pHLH with refractory, recurrent or progressive disease or intolerance with conventional HLH therapy.

The FDA approval was based on data from study NI-0501-03, interim data from the pivotal study NI-0501-04 and interim data from the long-term follow-up study NI-0501-05.

Study NI-0501-03 was a phase 1 randomized double-blinded placebo-controlled single ascending dose study, in 20 healthy adult volunteers investigating the safety, tolerability and pharmacokinetic (PK) profiles of single intravenous (IV) administrations of emapalumab took place between September 2011 and January 2013. During this study, 6 subjects received placebo, while 3, 3, 4, and 4 subjects (in total 14 subjects) received emapalumab doses of 0.01, 0.1, 1, and 3 mg/kg, respectively.

Emapalumab PK data from healthy volunteers were evaluated using a population modeling approach. The PK of emapalumab was best described by a two-compartment model (NI-0501-03 - Modelling and Simulation support to NI-0501 PK analysis of study NI-0501-03). In healthy volunteers, emapalumab has the typical PK profile expected for a mAb, with low central and peripheral volumes of distribution (3.02 L and 2.83 L), slow clearance (0.007 L/h) and long distribution and terminal half-lives (1.55 and 25.4 days).

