In placebo-treated subjects, mean total IFN γ levels (which represents free IFN γ in the absence of emapalumab) ranged from 60.09 pg/mL to 125.2 pg/mL, showing no visible trend over time. In contrast, in subjects on emapalumab, total IFN γ levels (which to the majority represents IFN γ bound to emapalumab due to the marked emapalumab molar excess of IFN γ) started to increase within 24 hours post-dosing. The maximal mean level of total IFN γ of 1013.6 pg/mL was reached at Week 8 post-dosing for the subjects who received a dose of 1 mg/kg and maximal mean level of 1011.2 pg/mL was reached at Week 4 post-dosing for the subjects who received a dose of 3 mg/kg.

The infusions of emapalumab were well tolerated and the effects observed during the 8-week monitoring after drug infusion did not reveal any serious or unexpected off target safety or immunogenicity concerns. A Herpes Zoster was reported as a serious adverse reaction in the highest dose group (3 mg/kg). Its intensity was moderate and healed with antiviral therapy. The subject recovered with no sequelae. An increased susceptibility to HZ infections in patients having developed auto-antibodies against IFN γ (23) or having received ustekinumab (a monoclonal antibody which decreases IFN γ production by inhibiting the p40 subunit of IL-12) has been described in the literature (24).

In conclusion, no safety signal emerged from the safety parameters (AEs, clinical laboratory evaluations, vital signs and ECG analysis) collected during the follow-up period extended up to week 44 after emapalumab infusion. The tolerability/safety profile, as well as the PK characteristics observed after administration of emapalumab in healthy volunteers supported the continuation of the development program for emapalumab for the treatment of HLH.

Study NI-0501-04 was designed to investigate the safety and tolerability profile of multiple intravenous (IV) administrations of emapalumab and its efficacy in primary hemophagocytic lymphohistiocytosis (pHLH) patients. The evaluation of the pharmacokinetic (PK) profile and the pharmacodynamic (PD) effects of emapalumab is also an important objective of the study to define the appropriate therapeutic dose regimen for the treatment of pHLH patients. The study has been conducted according to twin protocols in EU and in the US.

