6.7.6.2 Calculations

The PD biomarkers (Total IFN γ , CXCL9 and sIL2R serum levels) will be described descriptively, and the change from base-line levels will be derived.

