### **3.3 Study endpoints**

#### **3.3.1 Primary endpoints**

The primary endpoints are as follows:

- PK parameters:  $C_{max}$ ,  $t_{max}$ , CEOI,  $AUC_{last}$ ,  $AUC_{inf}$ , % $AUC_{extr}$ ,  $\lambda_z$ ,  $t_{1/2}$ , CL,  $V_{ss}$ ,  $MRT_{last}$  and  $MRT_{inf}$ .
- PD biomarkers:
  - Pre-dose circulating IFN $\gamma$  concentration
  - Total IFN $\gamma$  concentrations
  - CXCL9 concentration
  - sIL2R concentration

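### Setting biomarker values below the LLOQ to 0 can bias the pre-dose IFNγ primary endpoint low, materially so if levels lie near the lower end of the earlier study's 60–125 pg/mL placebo means

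*SAP*

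**What the plan says.** SAP 14.2 (Table 6) lists pre-dose circulating IFNγ, total IFNγ, CXCL9 and sIL2R. Both IFNγ rows carry an LLOQ of 50 pg/mL ("concentration pg/mL 50.00 pg/mL 0.01"); sIL2R also has 50 and CXCL9 has 80 pg/mL. One handling rule for descriptive statistics follows the table: "Lower Limit of Quantification (LLOQ) will be substituted with 0". Read literally it replaces the limit itself; it must mean results below the limit. SAP 14.1 has the same rule for emapalumab.

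SAP 3.3.1 names the pre-dose measure ("Pre-dose circulating IFN"γ) among the primary endpoints. Under SAP 8.3.1 it is summarised by N, arithmetic mean, SD, median, minimum and maximum; the geometric mean is added for PK only. SAP 14.2.1 to 14.2.3 restrict the biomarker tables and plots to the emapalumab group, planned as 6 subjects, and 14.2.2 plots mean ± SD. For the biomarkers other than the pre-dose measure, Protocol 6.7.6.2 adds that "the change from base-line levels will be derived".

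Protocol 4.1.2.3 gives the only information on levels without drug. In placebo subjects of NI-0501-03, where total IFNγ stands for free IFNγ, mean levels "ranged from 60.09 pg/mL to 125.2 pg/mL, showing no visible trend over time".

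**The concern.** A drug concentration before dosing is truly zero, so replacing a non-quantifiable result by 0 does little harm there. IFNγ is endogenous. A result below 50 pg/mL means a level between 0 and 50, and the placebo data make a level of exactly 0 implausible. Replacing a positive value by 0 can only lower the mean, and it usually widens the SD.

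The documented placebo means lie at 60.09/50 = 1.20 to 125.2/50 = 2.50 times the LLOQ. At the lower end of that range, individual results below the limit would be common. Protocol 4.2 says that the study exists to compare PK and PD between Japanese and non-Japanese subjects. A baseline mean lowered by the substitution could look like a population difference or hide one. The SAP asks for no count of results below the limit, so the summary tables would not show how often the rule had acted.

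**Working it through.** The plan states no bias or precision figure for this endpoint, so there is none to reproduce.

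**Inputs from the documents.** LLOQ L = 50 pg/mL (SAP Table 6). Placebo means 60.09 to 125.2 pg/mL, midpoint (60.09 + 125.2)/2 = 92.6 (Protocol 4.1.2.3). Emapalumab subjects n = 6 (SAP 4.3). Highest mean total IFNγ after 1 mg/kg 1013.6 pg/mL (Protocol 4.1.2.3).

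**Assumptions.** Neither document gives an SD or CV for IFNγ. I take a lognormal distribution with between-subject CV 30%, 50% and 80%.

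**Bound without any distribution.** Each result set to 0 lowers a 6-subject mean by at most 50/6 = 8.3 pg/mL.

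**Formulas.** For true mean m:
- σ² = ln(1 + CV²), μ = ln m − σ²/2, a = (ln 50 − μ)/σ.
- Share below the limit: p = Φ(a). Chance of at least one among 6: 1 − (1 − p)^6.
- Expected mean when results below the limit are set to c: m[1 − Φ(a − σ)] + p·c, with c = 0 or 25 (LLOQ/2).
- Variance after substitution: m²(1 + CV²)[1 − Φ(a − 2σ)] + p·c² − (that mean)².

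**One case in full.** For m = 60.09 and CV 50%: σ = 0.4724, μ = 3.9843, a = −0.153, p = 0.439, Φ(a − σ) = 0.2659. With c = 0 the mean is 60.09 × (1 − 0.2659) = 44.1, a bias of −26.6%. With c = 25 it is 44.1 + 0.439 × 25 = 55.1, a bias of −8.3%.

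**All cases.** The SD ratio is the SD after substitution divided by the true SD.

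| True mean | CV | Share <50 | ≥1 of 6 | Mean with 0 | Mean with 25 | SD ratio, 0 / 25 |
|---|---|---|---|---|---|---|
| 60.09 | 30% | 32% | 90% | 46.9 (−22.0%) | 54.8 (−8.8%) | 1.90 / 1.32 |
| 60.09 | 50% | 44% | 97% | 44.1 (−26.6%) | 55.1 (−8.3%) | 1.47 / 1.12 |
| 60.09 | 80% | 54% | 99% | 43.9 (−27.0%) | 57.3 (−4.7%) | 1.22 / 1.02 |
| 92.6 | 30% | 2.5% | 14% | 91.5 (−1.2%) | 92.1 (−0.5%) | 1.10 / 1.04 |
| 92.6 | 50% | 14% | 60% | 86.9 (−6.2%) | 90.5 (−2.3%) | 1.17 / 1.06 |
| 92.6 | 80% | 30% | 88% | 82.5 (−11.0%) | 90.0 (−2.9%) | 1.12 / 1.03 |
| 125.2 | 30% | 0.1% | 1% | 125.1 (−0.1%) | 125.2 (0.0%) | 1.00 / 1.00 |
| 125.2 | 50% | 4% | 24% | 123.4 (−1.5%) | 124.5 (−0.6%) | 1.05 / 1.02 |
| 125.2 | 80% | 17% | 67% | 119.1 (−4.9%) | 123.3 (−1.5%) | 1.06 / 1.02 |

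LLOQ/2 is at least as close to the true mean as 0 in every row.

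**Change from baseline.** With a true baseline of 60.09 and CV 50%, the rise to 1013.6 is 953.5; with the baseline mean lowered to 44.1 it is 969.5. The ratio 969.5/953.5 = 1.017 is an overstatement of 1.7%. That is the largest value, to one decimal, over the nine cases.

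**Median.** At m = 60.09, the chance that 3 or more of 6 results fall below the limit is 29%, 54% and 72% for CV 30%, 50% and 80%. With more than half below, the median is the substituted constant, whichever constant is chosen.

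**The case against.** The best case for leaving the rule alone is that its effect may be small and visible. The placebo figures are time-point means from another study ("During this study, 6 subjects received placebo, while 3, 3, 4, and 4 subjects (in total 14 subjects) received emapalumab"), not individual levels in this population. No SD, no share below 50 pg/mL and no LLOQ is given for that study. If Japanese baselines resemble the upper end of the range, the bias is 5% or less. The median, minimum and maximum stand beside the mean, a minimum of 0 would betray the substitution, every value is listed, and no test or sample size depends on this mean. LLOQ/2 is itself an arbitrary constant. All of this stands. It limits the severity but gives no reason to choose an implausible value over a less biased one at the same cost.

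A reader might infer more than the documents support:
- That IFNγ is known to lie just above the limit, so that the endpoint is biased low. Only the lower end of the range is that close, and the bias arises only if some pre-dose results fall below 50.
- That the post-dose response is seriously exaggerated. The absolute change moves by under 2%. A fold rise would move from about 17 (1013.6/60.09) to about 23 (1013.6/44.1), but neither document plans a ratio to baseline.
- That suppression of CXCL9 would be overstated, or sIL2R distorted. The documents give no level for either marker.
- That the median solves the problem. It does not once half or more of the results are below the limit.

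**Conclusion.** The point holds as a conditional one. The rule treats an endogenous analyte, measurable "in the absence of emapalumab", as though it could be absent. The direction is certain whenever a pre-dose result falls below 50 pg/mL: the mean of a primary endpoint goes down. In the cases examined the SD rises or is essentially unchanged, by a factor of 1.2 to 1.9 at a true mean of 60.

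The size is not certain. It is about a quarter of the mean if true levels are near 60 pg/mL, moderate at the midpoint, and negligible to 5% near 125. These figures rest on the lognormal shape, the assumed CVs and the relevance of the earlier placebo means. The point should be corrected, but no formal conclusion of the study depends on it.

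**What to change.** In SAP 14.2, for the pharmacodynamic biomarkers only, replace the rule by: values below the LLOQ will be set to LLOQ/2 for descriptive statistics. That is 25 pg/mL for both IFNγ measures and sIL2R, and 40 pg/mL for CXCL9. This wording also removes the ambiguity about what is being replaced.

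Add to the biomarker tables the number and percentage of values below the LLOQ at each time point. Where half or more of the values are below it, report the mean and median as not reliably estimable, and show the median as '<LLOQ' when more than half are. Keep 0 for emapalumab concentrations in SAP 14.1.

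The cost is two or three SAP sentences and one table column, with no new samples, visits or data. The downside is that LLOQ/2 is also an assumption; the count below the LLOQ lets the reader see how much rests on it.
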